Appendix 3 Criteria for Identifying ECG Measurements of Potential Clinical Relevance

Variable	Criterion Value ^a	Change Relative to Baseline ^a
Heart Rate	≥120 bpm	Increase of ≥15 bpm
Heart Rate	≤50 bpm	Decrease of ≥15 bpm
PR	>200 msec	Increase of ≥50 msec
QRS	≥120 msec	Increase of ≥20 msec

[figure not shown]
^aIn order to be identified as potentially clinically relevant, an on-treatment value must meet the “Criterion Value” and also represent a change from the subject’s baseline value of at least the magnitude shown in the “Change Relative to Baseline” column.

[figure not shown]
Appendix 4

[figure not shown]
Preferred Terms for Statins and Ezetimibe

Drug	EDC Option for Drug Name (English)	Preferred Term WHODD Drug Name	Preferred Term WHODD Drug Code	WHODD Drug Code 6 Digits
Statins	Pravastatin sodium	PRAVASTATIN SODIUM	00880402001	008804
	Simvastatin	SIMVASTATIN	00848101001	008481
	Rosuvastatin calcium	ROSVASTATIN CALCIUM	01588602001	015886
	Pitavastatin calcium	PITAVASTATIN CALCIUM	06470002001	064700
	Atorvastatin calcium	ATORVASTATIN CALCIUM	01326102001	013261
	Fluvastatin sodium	FLUVASTATIN SODIUM	01224502001	012245
	Caduet No. 1	AMLODIPINE BESILATE; ATORVASTATIN CALCIUM	12872303001	128723
	Caduet No. 2	AMLODIPINE BESILATE; ATORVASTATIN CALCIUM	12872303001	128723
	Caduet No. 3	AMLODIPINE BESILATE; ATORVASTATIN CALCIUM	12872303001	128723
	Caduet No. 4	AMLODIPINE BESILATE; ATORVASTATIN CALCIUM	12872303001	128723
	Amaluet No. 1	AMLODIPINE BESILATE; ATORVASTATIN CALCIUM TRIHYDRATE	12872304001	128723
	Amaluet No. 2	AMLODIPINE BESILATE; ATORVASTATIN CALCIUM TRIHYDRATE	12872304001	128723
	Amaluet No. 3	AMLODIPINE BESILATE; ATORVASTATIN CALCIUM TRIHYDRATE	12872304001	128723
	Amaluet No. 4	AMLODIPINE BESILATE; ATORVASTATIN CALCIUM TRIHYDRATE	12872304001	128723
	Atozet LD	ATORVASTATIN CALCIUM; EZETIMIBE	12872002001	128720
	Atozet HD	ATORVASTATIN CALCIUM; EZETIMIBE	12872002001	128720
	Rosuzet LD	EZETIMIBE; ROSUVASTATIN CALCIUM	10641002001	106410
	Rosuzet HD	EZETIMIBE; ROSUVASTATIN CALCIUM	10641002001	106410
Ezetimibe	Ezetimibe	EZETIMIBE	01587001001	015870
	Atozet LD	ATORVASTATIN CALCIUM; EZETIMIBE	12872002001	128720
	Atozet HD	ATORVASTATIN CALCIUM; EZETIMIBE	12872002001	128720

Drug	EDC Option for Drug Name (English)	Preferred Term WHODD Drug Name	Preferred Term WHODD Drug Code	WHODD Drug Code 6 Digits
	Rosuzet LD	EZETIMIBE; ROSVASTATIN CALCIUM	10641002001	106410
	Rosuzet HD	EZETIMIBE; ROSVASTATIN CALCIUM	10641002001	106410

Appendix 6 List of Figures and Tables

CT-1.2-1 Subject Disposition During Treatment Period (Randomized Subjects)

CT-1.2-2 Subject Disposition During Treatment Period by Statin Response (Randomized Subjects)

CT-1.3-1 Analysis Set (Randomized Subjects)

CT-1.3-2 Analysis Set by Statin Response (Randomized Subjects)

CT-2.2-1 Reasons for Discontinuation During Treatment Period (Randomized Subjects)

CT-2.2-2 Reasons for Discontinuation During Treatment Period by Statin Response (Randomized Subjects)

CT-2.3-1 Summary of Major Protocol Deviations by Type of Deviation (Randomized Subjects)

CT-2.3-2 Summary of Major Protocol Deviations by Type of Deviation by Statin Response (Randomized Subjects)

CT-3.1.1-1 Demographic and Baseline Characteristics (Full Analysis Set)

CT-3.1.1-2 Demographic and Baseline Characteristics by Statin Response (Full Analysis Set)

CT-3.1.2-1 Demographic and Baseline Characteristics (Safety Analysis Set)

CT-3.1.2-2 Demographic and Baseline Characteristics by Statin Response (Safety Analysis Set)

CT-3.1.3-1 Demographic and Baseline Characteristics (Pharmacokinetic Analysis Set)

CT-3.1.3-2 Demographic and Baseline Characteristics by Statin Response (Pharmacokinetic Analysis Set)

CT-3.2.1-1 Baseline Disease Characteristics (Full Analysis Set)

- CT-3.2.1-2 Baseline Disease Characteristics by Statin Response (Full Analysis Set)
- CT-3.2.2-1 Baseline Disease Characteristics (Safety Analysis Set)
- CT-3.2.2-2 Baseline Disease Characteristics by Statin Response (Safety Analysis Set)
- CT-3.3.1 Statin Intolerance Symptoms and Medications (Full Analysis Set with Statin Intolerance)
- CT-3.3.2 Statin Intolerance Symptoms and Medications (Safety Analysis Set with Statin Intolerance)
- CT-4.1.1-1 Prior Medications (Full Analysis Set)
- CT-4.1.1-2 Prior Medications by Statin Response (Full Analysis Set)
- CT-4.1.2-1 Concomitant Medications (Full Analysis Set)
- CT-4.1.2-2 Concomitant Medications by Statin Response (Full Analysis Set)
- CT-4.2-1 Concomitant Hypercholesterolemic Treatment Medications (Full Analysis Set)
- CT-4.2-2 Concomitant Hypercholesterolemic Treatment Medications by Statin Response (Full Analysis Set)
- CT-5.1 Primary Analysis: Percent Change from Baseline in LDL-C at Week 12 (ANCOVA) (Full Analysis Set)
- CT-5.2 Percent Change from Baseline in LDL-C at each Visit (ANCOVA) (Full Analysis Set)
- CT-5.3 Dose Response: Percent Change from Baseline in LDL-C at Week 12 (Full Analysis Set)
- CT-5.4 Sensitivity Analysis: Percent Change from Baseline in LDL-C at each Visit (MMRM) (Full Analysis Set)
- CT-6.1 Percent Change from Baseline in Secondary Efficacy Parameters (ANCOVA) (Full Analysis Set)
- CT-6.2.1-1 Incidence of Subjects who achieved the target value in LDL-C (Full Analysis Set)
- CT-6.2.1-2 Incidence of Subjects who achieved the target value in LDL-C by Statin Response (Full Analysis Set)
- CT-6.2.2-1 Incidence of Subjects who achieved < 70 mg/dL in LDL-C (Full Analysis Set)

CT-6.2.2-2 Incidence of Subjects who achieved < 70 mg/dL in LDL-C by Statin Response (Full Analysis Set)

CT-6.3-1 Descriptive Statistics for Efficacy Parameters Values, Change and Percent Change from Baseline by Visit (Full Analysis Set)

CT-6.3-2 Descriptive Statistics for Efficacy Parameters Values, Change and Percent Change from Baseline by Visit by Statin Response (Full Analysis Set)

CT-6.4.1 Subgroup Analysis: Percent Change from Baseline in LDL-C at Week 12 (ANCOVA) by Statin Response (Full Analysis Set)

CT-6.4.2 Subgroup Analysis: Percent Change from Baseline in LDL-C at Week 12 (ANCOVA) by Sex (Full Analysis Set)

CT-6.4.3 Subgroup Analysis: Percent Change from Baseline in LDL-C at Week 12 (ANCOVA) by Familial Hypercholesterolemia (Full Analysis Set)

CT-6.4.4 Subgroup Analysis: Percent Change from Baseline in LDL-C at Week 12 (ANCOVA) by Diabetes Mellitus (Full Analysis Set)

CT-6.4.5 Subgroup Analysis: Percent Change from Baseline in LDL-C at Week 12 (ANCOVA) by Age in Category (Full Analysis Set)

CT-6.4.6 Subgroup Analysis: Percent Change from Baseline in LDL-C at Week 12 (ANCOVA) by Statin Therapy (Full Analysis Set)

CT-7.1-1 Extent of Exposure to Investigational Medicinal Product (Safety Analysis Set)

CT-7.1-2 Extent of Exposure to Investigational Medicinal Product by Statin Response (Safety Analysis Set)

CT-7.2.1-1 Treatment Compliance (Full Analysis Set)

CT-7.2.1-2 Treatment Compliance by Statin Response (Full Analysis Set)

CT-7.2.2-1 Treatment Compliance (Safety Analysis Set)

CT-7.2.2-2 Treatment Compliance by Statin Response (Safety Analysis Set)

CT-7.2.3-1 Hypercholesterolemic Treatment Compliance (Full Analysis Set)

CT-7.2.3-2 Hypercholesterolemic Treatment Compliance by Statin Response (Full Analysis Set)

CT-8.1-1 Overall Summary of Adverse Event (Safety Analysis Set)

- CT-8.1-2 Overall Summary of Adverse Event by Statin Response (Safety Analysis Set)
- CT-8.2-1 Incidence of TEAEs by MedDRA System Organ Class and Preferred Term (Safety Analysis Set)
- CT-8.2-2 Incidence of TEAEs by MedDRA System Organ Class and Preferred Term by Statin Response (Safety Analysis Set)
- CT-8.2-3 Incidence of TEAEs Occurring in ≥ 2 subjects of Any Group by MedDRA System Organ Class and Preferred Term (Safety Analysis Set)
- CT-8.2-4 Incidence of TEAEs Occurring in ≥ 2 subjects of Any Group by MedDRA System Organ Class and Preferred Term by Statin Response (Safety Analysis Set)
- CT-8.3-1 Incidence of IMP-related TEAEs by MedDRA System Organ Class and Preferred Term (Safety Analysis Set)
- CT-8.3-2 Incidence of IMP-related TEAEs by MedDRA System Organ Class and Preferred Term by Statin Response (Safety Analysis Set)
- CT-8.3-3 Incidence of IMP-related TEAEs Occurring in ≥ 2 subjects of Any Group by MedDRA System Organ Class and Preferred Term (Safety Analysis Set)
- CT-8.3-4 Incidence of IMP-related TEAEs Occurring in ≥ 2 subjects of Any Group by MedDRA System Organ Class and Preferred Term by Statin Response (Safety Analysis Set)
- CT-8.4-1 Incidence of TEAEs by Severity by MedDRA System Organ Class and Preferred Term (Safety Analysis Set)
- CT-8.4-2 Incidence of TEAEs by Severity by MedDRA System Organ Class and Preferred Term by Statin Response (Safety Analysis Set)
- CT-8.5-1 Incidence of IMP-related TEAEs by Severity by MedDRA System Organ Class and Preferred Term (Safety Analysis Set)
- CT-8.5-2 Incidence of IMP-related TEAEs by Severity by MedDRA System Organ Class and Preferred Term by Statin Response (Safety Analysis Set)
- CT-8.6-1 Incidence of TEAEs with an Outcome of Death by MedDRA System Organ Class and Preferred Term (Safety Analysis Set)
- CT-8.6-2 Incidence of TEAEs with an Outcome of Death by MedDRA System Organ Class and Preferred Term by Statin Response (Safety Analysis Set)

CT-8.7-1 Incidence of IMP-related TEAEs with an Outcome of Death by MedDRA System Organ Class and Preferred Term (Safety Analysis Set)

CT-8.7-2 Incidence of IMP-related TEAEs with an Outcome of Death by MedDRA System Organ Class and Preferred Term by Statin Response (Safety Analysis Set)

CT-8.8-1 Incidence of Serious TEAEs by MedDRA System Organ Class and Preferred Term (Safety Analysis Set)

CT-8.8-2 Incidence of Serious TEAEs by MedDRA System Organ Class and Preferred Term by Statin Response (Safety Analysis Set)

CT-8.9-1 Incidence of IMP-related Serious TEAEs by MedDRA System Organ Class and Preferred Term (Safety Analysis Set)

CT-8.9-2 Incidence of IMP-related Serious TEAEs by MedDRA System Organ Class and Preferred Term by Statin Response (Safety Analysis Set)

CT-8.10-1 Incidence of TEAEs Leading to Discontinuation of Investigational Medicinal Product Administration by MedDRA System Organ Class and Preferred Term (Safety Analysis Set)

CT-8.10-2 Incidence of TEAEs Leading to Discontinuation of Investigational Medicinal Product Administration by MedDRA System Organ Class and Preferred Term by Statin Response (Safety Analysis Set)

CT-8.11-1 Incidence of IMP-related TEAEs Leading to Discontinuation of Investigational Medicinal Product Administration by MedDRA System Organ Class and Preferred Term (Safety Analysis Set)

CT-8.11-2 Incidence of IMP-related TEAEs Leading to Discontinuation of Investigational Medicinal Product Administration by MedDRA System Organ Class and Preferred Term by Statin Response (Safety Analysis Set)

CT-8.12-1 Incidence of AESIs by MedDRA System Organ Class and Preferred Term (Safety Analysis Set)

CT-8.12-2 Incidence of AESIs by MedDRA System Organ Class and Preferred Term by Statin Response (Safety Analysis Set)

CT-8.13-1 Incidence of IMP-related AESIs by MedDRA System Organ Class and Preferred Term (Safety Analysis Set)

CT-8.13-2 Incidence of IMP-related AESIs by MedDRA System Organ Class and Preferred Term by Statin Response (Safety Analysis Set)

- CT-9.1 Listing of Deaths (Safety Analysis Set)
- CT-9.2 Listing of Serious Adverse Events Other Than Death (Safety Analysis Set)
- CT-9.3 Listing of Discontinuations Due to Adverse Events
- CT-10.1.1-1 Descriptive Statistics for Clinical Laboratory Test Results - Serum Chemistry
- CT-10.1.1-2 Descriptive Statistics for Clinical Laboratory Test Results by Statin Response - Serum Chemistry (Safety Analysis Set)
- CT-10.1.2-1 Descriptive Statistics for Clinical Laboratory Test Results - Hematology (Safety Analysis Set)
- CT-10.1.2-2 Descriptive Statistics for Clinical Laboratory Test Results by Statin Response - Hematology (Safety Analysis Set)
- CT-10.1.3-1 Descriptive Statistics for Clinical Laboratory Test Results - Urinalysis (Safety Analysis Set)
- CT-10.1.3-2 Descriptive Statistics for Clinical Laboratory Test Results by Statin Response - Urinalysis (Safety Analysis Set)
- CT-10.2.1-1 Shift Tables of Clinical Laboratory Test Results - Serum Chemistry (Safety Analysis Set)
- CT-10.2.1-2 Shift Tables of Clinical Laboratory Test Results by Statin Response - Serum Chemistry (Safety Analysis Set)
- CT-10.2.2-1 Shift Tables of Clinical Laboratory Test Results - Hematology (Safety Analysis Set)
- CT-10.2.2-2 Shift Tables of Clinical Laboratory Test Results by Statin Response - Hematology (Safety Analysis Set)
- CT-10.2.3-1 Shift Tables of Clinical Laboratory Test Results - Urinalysis (Safety Analysis Set)
- CT-10.2.3-2 Shift Tables of Clinical Laboratory Test Results by Statin Response - Urinalysis (Safety Analysis Set)
- CT-10.2.4-1 Shift Tables of Clinical Laboratory Test Results - Qualitative Urinalysis (Safety Analysis Set)
- CT-10.2.4-2 Shift Tables of Clinical Laboratory Test Results by Statin Response - Qualitative Urinalysis (Safety Analysis Set)

- CT-10.3-1 Incidences of Potentially Clinically Significant Abnormalities in Laboratory Tests (Safety Analysis Set)
- CT-10.3-2 Incidences of Potentially Clinically Significant Abnormalities in Laboratory Tests by Statin Response (Safety Analysis Set)
- CT-10.4 Listing of Abnormal Laboratory Findings (Safety Analysis Set)
- CT-11.1-1 Descriptive Statistics for Vital Signs (Safety Analysis Set)
- CT-11.1-2 Descriptive Statistics for Vital Signs by Statin Response (Safety Analysis Set)
- CT-11.2-1 Incidences of Potentially Clinically Significant Abnormalities in Vital Signs (Safety Analysis Set)
- CT-11.2-2 Incidences of Potentially Clinically Significant Abnormalities in Vital Signs by Statin Response (Safety Analysis Set)
- CT-11.3-1 Descriptive Statistics for Body Weight (Safety Analysis Set)
- CT-11.3-2 Descriptive Statistics for Body Weight by Statin Response (Safety Analysis Set)
- CT-11.4-1 Incidences of Potentially Clinically Significant Abnormalities in Body Weight (Safety Analysis Set)
- CT-11.4-2 Incidences of Potentially Clinically Significant Abnormalities in Body Weight by Statin Response (Safety Analysis Set)
- CT-12.1-1 Descriptive Statistics for ECG Parameters (Safety Analysis Set)
- CT-12.1-2 Descriptive Statistics for ECG Parameters by Statin Response (Safety Analysis Set)
- CT-12.2-1 Categorical Analysis of ECG - QTcF (Safety Analysis Set)
- CT-12.2-2 Categorical Analysis of ECG - QTcF by Statin Response (Safety Analysis Set)
- CT-12.3-1 Shift Table of ECG Findings (Normal/Abnormal Assessments) (Safety Analysis Set)
- CT-12.3-2 Shift Table of ECG Findings (Normal/Abnormal Assessments) by Statin Response (Safety Analysis Set)
- CT-12.4-1 Incidences of Potentially Clinically Significant Abnormalities in ECG Parameters (Safety Analysis Set)

CT-12.4-2 Incidences of Potentially Clinically Significant Abnormalities in ECG Parameters by Statin Response (Safety Analysis Set)

CF-1-1 Percent Change from Baseline by Visit in Efficacy Parameters (LSMean+-SE) (Full Analysis Set)

CF-1-2 Percent Change from Baseline by Visit in Efficacy Parameters (LSMean+-SE) by Statin Response (Full Analysis Set)

CF-2-1 Percent Change from Baseline by Visit in Efficacy Parameters (Mean+-SD) (Full Analysis Set)

CF-2-2 Percent Change from Baseline by Visit in Efficacy Parameters (Mean+-SD) by Statin Response (Full Analysis Set)

PKT-1.1 Individual and Summary of ETC-1002 Plasma Concentrations Following Oral Administration of ETC-1002 (Pharmacokinetic Analysis Set)

PKT-1.2 Individual and Summary of ESP15228 Plasma Concentrations Following Oral Administration of ETC-1002 (Pharmacokinetic Analysis Set)

PKF-1.1 Mean ETC-1002 Plasma Concentrations at Pre-dose Following Oral Administration of ETC-1002 (Pharmacokinetic Analysis Set)

PKF-1.2 Mean ESP15228 Plasma Concentrations at Pre-dose Following Oral Administration of ETC-1002 (Pharmacokinetic Analysis Set)

PKF-2.1 Individual ETC-1002 Plasma Concentrations at Pre-dose Following Oral Administration of ETC-1002 (Pharmacokinetic Analysis Set)

PKF-2.2 Individual ESP15228 Plasma Concentrations at Pre-dose Following Oral Administration of ETC-1002 (Pharmacokinetic Analysis Set)

Appendix 7	List of Subject Data Listings
DREAS-1	Discontinued Subjects and Reason for Discontinuation (Screened Subjects)
SUBEX-1	Subjects Excluded From Analysis Set (Randomized Subjects)
DEMOG-1	Demographic Characteristics (Screened Subjects)
SMED-1	Investigational Medicinal Product Compliance (Screened Subjects)
SMED-2.1	Prior Hypercholesterolemic Treatment (Screened Subjects)
SMED-2.2	Hypercholesterolemic Treatment Compliance (Screened Subjects)
EFF-1.1	Listing of Primary Efficacy Endpoint - LDL-C (Randomized subject)
EFF-1.2	Listing of Efficacy Endpoints Other Than LDL-C (Randomized subject)
AE-1	Adverse Events (Screened Subjects)
LAB-1 .1	Laboratory Values (Hematology) (Screened Subjects)
LAB-1 .2	Laboratory Values (Blood Chemistry) (Screened Subjects)
L AB-1.3	Laboratory Values (Urinalysis) (Screened Subjects)
LAB-2	Laboratory Values (Fasting Lipid) (Screened Subjects)
PDATA-1	Study Completion Status and Reason for Discontinuation (Screened Subjects)
PDATA-2	Inclusion Criteria and Exclusion Criteria Not Met
PDATA-3.1	Medical History (Hypercholesterolemia) (Screened Subjects)
PDATA-3.2	Medical History (Screened Subjects)
PDATA-4	Physical Examination (Screened Subjects)
PDATA-5.1	Prior and Concomitant Medication (Screened Subjects)
PDATA-5.2	Prior and Concomitant Therapy (Screened Subjects)
PDATA-6	Vital Signs and Body Weight (Screened Subjects)
PDATA-7	12-Lead ECG Parameters and Findings (Screened Subjects)
PDATA-8	Blood Draw Time for Pharmacokinetics (Randomized Subjects)
PDATA-9	Pregnancy Test (Screened Subjects)
PDATA-10	TSH and Virus Test (Screened Subjects)

Protocol 346-102-00001

- PDATA-11 Blood Draw Time for Biomarker and DNA storage (Screened Subjects)
- PDATA-12 Screen Failures
- PDATA-13 Post-treatment Follow-up (Randomized Subjects)
- PDEV-1 Protocol Deviations (Screened Subjects)

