6.1.2 Treatment Period

Subjects who are randomized and proceed to the treatment period will continue to receive hypercholesterolemia drugs that have been taken from before informed consent without changing the type or the dose and regimen [REDACTED]. Subjects will also orally receive ETC-1002 60 mg/day, 120 mg/day, 180 mg/day, or placebo. The time of IMP administration should be same to the extent possible. The following information will be recorded in the eCRF: number of tablets taken per day, start and end dates of administration as for the IMP; and name of the drug, route of administration, dose and frequency, daily dose, start and end dates of administration as for hypercholesterolemia drugs. Subjects with less than 80% compliance with IMP between scheduled visits will be withdrawn from the trial. The IMP compliance rate will be calculated using the

following formula. For information regarding the dose regimen and treatment period for each treatment group of the trial, see [Section 4.1](#).

$$\text{IMP compliance rate (\%)} = \frac{\text{Actual number of days of taking 3 tablets of the IMP}}{\text{Number of days from the previous visit to the day before the current visit}} \times 100$$

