3.4 Trial Visit Window

Data observed at CRF Visit will be used at each analysis visit (but data at discontinuation will not be used in analysis). Data from unscheduled visits will not be used. Efficacy analysis will be performed using the data obtained up until 2 days after final IMP administration. In assessment of efficacy endpoints, baseline for fasting lipid parameters is defined as the mean of the values for Day 1 (Visit T1) and Week -1 (Visit S3). If only one value is obtained, that value will be used as baseline. For efficacy endpoints other than fasting lipid parameters, baseline is defined as the value for Day 1 (Visit T1). For safety endpoints, baseline is defined as the last data obtained prior to initial IMP administration in the treatment period.

4 Sample Size

Differences in the percent change in LDL-C from baseline to Week 12 in the ETC-1002 group versus the placebo group in non-Japanese phase 3 trials were -18.1% and -17.42% in trials in statin tolerant subjects and -21.41% and -28.45% in trials in statin intolerant subjects. Based on the results, the difference between the ETC-1002 group and the placebo group in the subjects with statin tolerance was assumed to be 17% , and the difference between the ETC-1002 group and the placebo group in the subjects with statin intolerance was assumed to be 25% . For the present trial it was assumed that the percentage of statin intolerant subjects enrolled would be 20% and that the difference in the endpoint between the ETC-1002 group and the placebo group would be 19% in the overall trial population. Based on the results of the phase 3 trials, assuming a difference of 19% with standard deviation of 25% between the ETC-1002 groups and the placebo group in the percent change in LDL-C from baseline to Week 12, 38 subjects per group are required to achieve a power of 90% or higher in a two-tailed test with a 5% significance level. Assuming a withdrawal rate of 12.5% , the target number of subjects to be randomized was set at 44 per group.

5 Statistical Analysis Datasets

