5.4 Handling of Missing Data

In the primary analysis of the primary endpoint, when the LDL-C value at Week 12 is missing, the missing value will be imputed using the last value observed from after initial IMP administration up until 2 days after final IMP administration (last observation carried forward: LOCF).

In analysis of the percent change from baseline to Week 12 for secondary endpoints and of the proportion of subjects achieving the lipid management goals of LDL-C, missing values will be handled in the same manner as above. Missing values will not be imputed for sensitivity analysis and pharmacokinetic analysis.

Fasting lipid parameters will be handled as shown in the table below.

Condition	Fasting Lipid Parameters
Parameter to be used in analysis, irrespective of fasting condition	LDL-C (direct measurement)
Parameters to be used in analysis only when obtained under a fasting condition	LDL-C (Friedewald formula), HDL-C, non-HDL-C, TC, TG

6 Primary and Secondary Outcome Variables

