8.1.2 Sensitivity Analyses

A mixed-effects model repeated measures (MMRM) analysis assuming missing at random will be performed using OC data to calculate the least squares mean for each treatment group and the differences in the mean of the least squares between each ETC-

1002 group and the placebo group, together with the two-sided 95% confidence intervals, for the percent change in LDL-C from baseline at each visit (Week 2, Week 4, Week 6, Week 8, and Week 12). The MMRM model will include treatment group, the randomization stratification factor, visit, and treatment group-by-visit interaction as factors and baseline and baseline-by-visit interaction as covariates using an unstructured error covariance matrix. The Kenward-Roger method will be used to calculate the degree of freedom. If the MMRM procedure fails to converge in variance component estimation, the following error covariance structures will be used in the order of 1) heterogeneous toeplitz, 2) heterogeneous autoregressive of order 1, and 3) heterogeneous compound symmetry, and the first structure to yield convergence will be used. If a structure other than unstructured is selected, a sandwich estimator of standard error will be used.

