8.2 Secondary Efficacy Analyses

Secondary efficacy endpoints are the percent change from baseline to Week 12 in each assessment parameter (HDL-C, non-HDL-C, TC, TG, apo B, hsCRP, and HbA1c), the proportion of subjects whose LDL-C value achieves the lipid management goal based on risk assessment at Week 12, and the proportion of subjects whose LDL-C value achieves <70 mg/dL at Week 12.

For the percent change from baseline to Week 12 in each assessment parameter (HDL-C, non-HDL-C, TC, TG, apo B, hsCRP, and HbA1c), analysis of covariance will be performed using treatment group and the randomization stratification factor (statin tolerance/statin intolerance) as factors and the baseline value for each assessment parameter as a covariate. The least squares mean for each treatment group and the differences in the mean of the least squares between each ETC-1002 group and the placebo group, together with the two-sided 95% confidence intervals, will be calculated. The same analysis will also be performed for the percent change in each assessment parameter from baseline at each visit (Week 2, Week 4, Week 6, Week 8, and Week 12) using measured OC data. In addition to for the primary endpoint LDL-C, the timecourse of the least squares mean \pm standard error for the percent change from baseline in each assessment parameter (HDL-C, non-HDL-C, TC, TG, apoB, hsCRP, HbA1c, and LDL-C [calculated by Friedewald formula]) at each visit from baseline to Week 12 in the treatment period will be plotted for each treatment group. The same timecourses will also be plotted by the randomization stratification factor (statin response).

The proportion of subjects whose LDL-C value achieves the lipid management goal (<100 mg/dL [history of coronary artery disease or heterozygous familial hypercholesterolemia], <120 mg/dL [high risk], or <140 mg/dL [intermediate risk]) at Week 12, and the proportion of subjects whose LDL-C value achieves <70 mg/dL at Week 12 will be analyzed by Cochran-Mantel-Haenszel test stratified by statin response (statin tolerance/statin intolerance) to calculate the differences between each ETC-1002 group and the placebo group and the two-sided 95% confidence intervals (based on

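### By-visit LS means for the seven continuous secondary parameters come only from separate observed-case ANCOVAs, so withdrawal related to earlier response could bias the curves, and the differences from placebo, in either direction

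*SAP*

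**What the plan says.** **The figures.** SAP Appendix 6 lists "CF-1-1 Percent Change from Baseline by Visit in Efficacy Parameters (LSMean+-SE) (Full Analysis Set") and CF-1-2, the same by statin response. Neither entry names a model.

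**By-visit model, secondary parameters.** After the Week 12 ANCOVA, SAP 8.2 states: "The same analysis will also be performed for the percent change in each assessment parameter from baseline at each visit". The data source and the plot then follow directly: "using measured OC data. In addition to for the primary endpoint LDL-C, the timecourse of the least squares mean". The plot covers the seven continuous secondary parameters, LDL-C and Friedewald LDL-C. For Friedewald LDL-C, SAP 8.2 otherwise plans descriptive statistics only.

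**MMRM.** SAP 8.1.2 specifies it "for the percent change in LDL-C from baseline at each visit (Week 2, Week 4, Week 6, Week 8, and Week 12"). The output list has one MMRM table: "CT-5.4 Sensitivity Analysis: Percent Change from Baseline in LDL-C at each Visit (MMRM) (Full Analysis Set").

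**Which values count.** SAP 3.4: "Efficacy analysis will be performed using the data obtained up until 2 days after final IMP administration". The same section excludes values taken at discontinuation. Under SAP 5.4, HDL-C, non-HDL-C, TC, TG and Friedewald LDL-C are used only if the sample was fasting, while direct LDL-C is used regardless.

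**Week 12 secondary comparison.** SAP 5.4: "missing values will be handled in the same manner as above", which means LOCF, as for the primary analysis.

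**A mandated route out.** Protocol 6.1.2: "Subjects with less than 80% compliance with IMP between scheduled visits will be withdrawn from the trial".

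**The concern.** An observed case at a given visit is a subject still on treatment with a usable sample, so each plotted point describes a different and shrinking set of subjects. A separate ANCOVA at each visit adjusts for arm, statin response and baseline, but ignores the earlier on-treatment values of those who left. It is unbiased only if leaving is unrelated to response once those three are known. An MMRM uses the earlier values, so it also allows withdrawal to depend on responses already observed. The SAP provides that protection for LDL-C and for none of the seven other parameters.

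Selective withdrawal is plausible. Low compliance forces withdrawal and may be related to response. Deterioration of the underlying disease is a listed reason for discontinuation (Protocol 7.3.3). Sites receive an e-mail alert when LDL-C or TG passes a reference value (Protocol 8.8.1).

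At stake is the display of onset and maintenance of effect by dose. The time course of each parameter is a listed assessment (Protocol section 3), and characterising the dose-response is a primary objective.

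**Working it through.** **1. What feeds the figures.** Setting the SAP sections side by side:

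| Parameter | By-visit LS-mean models planned | Source of CF-1-1 |
|---|---|---|
| LDL-C (direct) | observed-case ANCOVA (8.1.1) and MMRM (8.1.2) | not stated; either fits |
| Seven continuous secondary parameters | observed-case ANCOVA (8.2) | not stated; only one candidate |
| Friedewald LDL-C | none | not stated; no candidate |

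For CF-1-2, the only within-stratum ANCOVA specified is LDL-C at Week 12 (SAP 8.3).

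**2. The plan's own figures.** Inputs from SAP section 4: difference 19, SD 25, two-sided 5%, power 90%, withdrawal 12.5%. Normal approximation: n = 2(1.960 + 1.282)² × (25/19)² = 36.4, so 37 per group. With the noncentral t, power is 89.7% at 37 and 90.5% at 38, so 38 is reproduced. 38/0.875 = 43.4, so 44 is reproduced.

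**3. Standard error of one difference.** 25 × √(2/44) = 5.33 with nobody missing. With 44 × 0.875 = 38.5 left per arm, 25 × √(2/38.5) = 5.70. About 5.5 is a fair yardstick.

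**4. Size under one plausible rule.** Simulation with four arms of 44, five visits, SD 25 and a true difference of −19 at every visit. Assumed: between-visit correlation of about 0.5 to 0.8, and a withdrawal hazard after each visit with logit a + b × (last value/25), the same rule in every arm. 4000 replicates; Monte Carlo error about 0.09. Week 12 observed-case results:

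| (a, b) | Placebo mean (truth 0), lower / higher correlation | Difference (truth −19), lower / higher correlation |
|---|---|---|
| (−3.3, 0.5) | −1.14 / −1.49 | −18.55 / −18.38 |
| (−3.5, 1.0) | −2.17 / −2.88 | −17.88 / −17.54 |
| (−4.0, 1.5) | −2.76 / −3.34 | −17.39 / −17.23 |

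The active-arm means shifted by −0.7 to −1.6. The shift in the difference runs from 19 − 18.55 = 0.45 to 19 − 17.23 = 1.77, and 1.77/5.5 = 0.32 of a standard error. A repeated-measures likelihood fit to the same data gave −18.83 to −19.24. Withdrawal was about 15 to 16% on placebo and 6 to 10.5% on active, so 8 to 12% overall; the largest shift comes from the setting furthest below the planned 12.5%.

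**5. Direction under other rules.** Two arms of 44, SD 25, effect rising over visits as 12, 17, 19, 19, 19, log-odds 1.0 per SD where withdrawal is selective, 1500 replicates (Monte Carlo error about 5.5/√1500 = 0.14). Week 12 difference, truth −19:

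| Who leaves (withdrawal placebo / active) | Observed case, correlation 0.5 / 0.7 | Likelihood fit, 0.5 / 0.7 |
|---|---|---|
| At random (13% / 13%) | −18.8 / −18.8 | −18.9 / −18.9 |
| Poor responders relative to own arm, both arms (about 12% each) | −19.0 / −18.9 | −19.1 / −19.0 |
| High absolute value, both arms (15% / 8%) | −18.1 / −17.9 | −18.9 / −19.0 |
| Poor responders, placebo only (24% / 0%) | −16.2 / −15.1 | −19.1 / −19.1 |
| Good responders, active only (0% / 24%) | −15.8 / −15.0 | −18.8 / −19.0 |
| Poor responders, active only (0% / 24%) | −22.0 / −23.0 | −19.0 / −19.0 |

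In the second row both curves drift by 1.3 to 1.9 points while the difference is unchanged. The one-arm rows are deliberate extremes.

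**The case against.** A reader might infer that poor responders will leave placebo, so that the placebo curve seems to improve and the difference from placebo shrinks. The documents do not support that. Nothing in them says who will leave or from which arm, and step 5 gives shrinkage, no change or widening according to the pattern. The shrinkage in step 4 is built in by making the hazard depend on the absolute value.

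The rest of the opposing case is strong on stakes:

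- **Masking.** Protocol 8.1 withholds all the lipid, apo B and hsCRP results from sites and sponsor during treatment and bars local measurement. This restricts response-driven withdrawal but does not exclude it, because of the LDL-C and TG alerts and the compliance rule.
- **Status of the figures.** They are descriptive. Protocol 9.4.1.5 plans only descriptive statistics by visit, and the formal Week 12 secondary comparison uses LOCF.
- **Existing checks.** Comparing CT-5.2 with CT-5.4 would reveal the problem for LDL-C, and indirectly for parameters that move with it. CT-6.3-1 gives counts by visit. These are partial checks: they can signal a bias but do not correct it in the other parameters.
- **Borrowed inputs.** SD 25 and effect 19 are for LDL-C. When withdrawal was made to depend on LDL-C and the analysed parameter was correlated 0.3 to 0.5 with it, the shift was about 0.5 to 0.8 points.

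Two further readings go too far. That CF-1-1 uses observed-case ANCOVA is a strong inference, not stated text. And the point concerns continuous parameters only: the goal-attainment proportions are not plotted as LS means.

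**Conclusion.** The point holds as a gap in the analysis plan with a modest likely effect. The seven continuous secondary parameters have no by-visit estimate that allows withdrawal to depend on earlier response, and Friedewald LDL-C has no stated LS-mean model at all. The second gap exists whatever the withdrawal pattern.

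Under a common absolute-value rule the Week 12 difference moves by about 0.4 to 1.8 points, at most about a third of a standard error. Lopsided withdrawal could move it by about 3 to 4 points either way; purely random withdrawal moves it not at all. These sizes rest on assumed correlations, selection strength and withdrawal patterns, and on LDL-C planning values; nothing has been computed on the scale of each secondary parameter.

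The primary test does not use these estimates, and neither do the Week 12 LOCF comparisons. That says nothing about whether LOCF itself is free of bias.

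**What to change.** In SAP 8.2, fit the SAP 8.1.2 MMRM (same fixed effects, Kenward-Roger, same covariance fallback) to each continuous secondary parameter and to Friedewald LDL-C, over the visits at which each is measured. Name it as the source of the LS mean ± SE in CF-1-1, for LDL-C as well. Tabulate by-visit differences from placebo with 95% confidence intervals, as CT-5.4 does for LDL-C. Keep the observed-case ANCOVAs as supportive.

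CF-1-2 needs more care. At the 20% minimum the intolerant stratum has 0.20 × 44 = 8.8, about 9 subjects per arm and 35 in all, against 5 × 6/2 = 15 covariance parameters for an unstructured five-visit fit. Apply the model by stratum, without the stratum term and with the fallback sequence. Where the stratum cannot support it, keep observed-case estimates and show the number of subjects at each visit.

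The cost is SAP wording and reuse of the printed PROC MIXED code for eight more variables, with no new data. The drawbacks are more output and a footnote saying that the plotted Week 12 value will differ from the LOCF and observed-case tables. The gain has a limit: each MMRM uses only that parameter's own history, so withdrawal driven by LDL-C is only partly accounted for in a parameter weakly correlated with it.
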